11. Qua	ality assurance and control	77
11.1.	Data collection	77
11.2	Trial monitoring	78
11.3	Audits and Inspection	79
12. Adr	ninistrative, ethical and regulatory aspects	80
12.1.	Conduct of the Study and Responsibilities	80
12.2.	Subject Information and Consent	81
12.3.	Regulatory Authorizations	81
12.4.	Authorization of the Biological Resource Center	82
12.5.	Processing of Research Data	82
12.6.	Amendments of the Protocol	82
12.7.	Sponsor Discontinuation Criteria	83
13. F	inancing and Insurance	83
13.1.	Financing of Research	83
13.2.	Insurance	83
14. Pub	olication policy and communication	84

14.1.	Publication policy	84
14.2.	Data sharing statements	85
14.3		85
15. Refei	rences	. 85

SYNOPSIS	
TITLE	A randomized phase III trial assessing a regorafenib- irinotecan combination (REGIRI) versus regorafenib alone in metastatic colorectal cancer patients after failure of standard therapies, according to the A/A genotype of Cyclin D1
SYNOPSIS VERSION	5.0
PATHOLOGY	Metastatic colorectal cancer
PROTOCOL CODES	Acronym: NEXT-REGIRI Sponsor Code: PROICM 2018-01 NEX EUDRACT: 2018-002231-24
STUDY SPONSOR	ICM – Institut régional du cancer de Montpellier Clinical, Translational and innovation Research Department [name] [name] Mail: [contact] [contact] [contact]
STUDY COORDINATOR	[name] ICM Digestive oncology [name] [contact] E-mail: [contact]
METHODOLOGY AND DATA MANAGEMENT CENTER	ICM - Institut régional du cancer de Montpellier Biometric Unit [name] Contact Name: [name] [contact] E-mail: [contact]
CLINICAL RESEARCH VIGILANCE UNIT	ICM - Institut régional du cancer de Montpellier [name] Contact Name: [name] [contact] E-mail: [contact]
STUDY DESIGN	Multicenter randomized Phase III study
NUMBER OF PLANNING PATIENT	78 patients out of about 312 screened patients

BACKGROUND AND RATIONALE

Patients with metastatic colorectal cancer (mCRC) who have received all approved standard treatments (except Regorafenib and TAS 102) no longer have treatment options available while maintaining a good performance status which would allow them to receive a new treatment.

A Phase III randomized trial that compared Nexiri (Nexavar® + Irinotecan) vs irinotecan or versus Sorafenib alone showed a progression-free survival at two-months which was favorable to the NEXIRI combination; 59% (IC95%: 39-66) versus 23% (IC95%: 10-33) and 22% (IC95%: 8-30) respectively.

The patients treated with Irinotecan or Sorafenib alone could receive NEXIRI combination after progression and the progression-free survivals were 3,7 months (IC95%: 2,2-4,9) and 3,5 months (IC95%: 2,1-3,7) in patients treated with NEXIRI or after progression and 1,9 months (IC95%: 1,7-2,1) and 2,1 months (IC95%: 1,9-2,5) in patients treated only with Irinotecan and Sorafenib respectively.

The median overall survival was higher with NEXIRI: 7,2 months (patients treated from the beginning of the study) and 7,9 months (patients treated after progression and crossover) versus 3 months in patients treated only with Irinotecan and 3,2 months in patients receiving only Sorafenib.

The A870A rs603965 polymorphism of cyclin D1, a molecule involved in the initiation of cell division, was favorable to the NEXIRI combination on overall survival with a median of 19.6 months versus 6.2 months for two other genotypes A/G and G/G.

Regorafenib, which is an oral signal deactivation agent with a chemical structure very similar to Sorafenib, is a standard treatment in heavily pretreated mCRC patients since the results of CORRECT study which compared Regorafenib to placebo on overall survival showed a superiority of Regorafenib: 6,4 months versus 5 months (HR 0,774 [IC95% 0,63, 0,94]).

Sorafenib isn't approved in mCRC so the objective of this NEXT-REGIRI trial is compared REGIRI combination (Regorafenib-Irinotecan) to Regorafenib alone in a phase III trial in patients in progression after having received all standard treatments and bearing genotype A/A of cyclin D1.

CTUDY OD IESTING	Drive any a bio ative
STUDY OBJECTIVES	Primary objective
	Comparison of overall survival in the Regorafenib and REGIRI
	combination (Regorafenib + Irinotecan) arms in mCRC patients of
	Cyclin D1 A/A genotype.
	Secondary objectives
	-Progression-free survival
	-Time to deterioration
	-Objective response rate
	-Disease control rate according to Recist criteria (version 1.1)
	-Toxicity (according to the NCI-CTCAE v5.0)
	-Quality of life (EORTC QLQ-C30)
STUDY ENDPOINTS	Primary endpoint:
	Overall survival presented with its median and confidence interval
	at 95%, estimated from randomization date to the date of death,
	whatever the cause, using the Kaplan-Meier method.
	Secondary endpoints: The accordary efficacy endpoint include:
	The secondary efficacy endpoint include:
	- Progression-free survival (PFS), defined as the time (days) from
	date of randomization to date of first observed disease
	progression (investigator's radiological or clinical assessment) or
	death due to any cause, if death occurs before progression is
	documented. Patients without tumor progression or death at the
	time of analysis will be censored at their last date of tumor
	assessment.
	- Time to Deterioration is defined as the time between the date of
	randomization and the first time the patient has a WHO ≥ 2 during
	treatment.
	- Disease control rate (DCR), defined as the rate of patients,
	whose best response was not progressive disease (i.e., CR, PR or
	SD), to all randomized patients in the treatment group
	- Objective response rate (OOR), defined as the rate of patients
	with CR or PR, to all randomized patients in the treatment group.
	Patients prematurely discontinuing without an assessment will be
	considered non-responders for the analysis.
	- Safety will be evaluated using the NCI-CTCAE version 5.0 scale;
	at each visit for the duration of the treatment.
	-Quality of life will be evaluated, using the EORTC QLQ-C30
	questionnaire.
	The expected benefit is an overall survival improvement of this
	treatment in patients with metastatic colorectal cancer who have
	received all standard treatments except TAS-102 and
	Regorafenib.

RISK AND BENEFITS	Toxicity and tolerance will be clinically and biologically assessed and rated on the NCIC CTCAE V5.0 scale at each visit. The expected benefit is an improvement in the overall survival of this treatment in patients with metastatic colorectal cancer who have received all standard treatments except TAS-102 and regorafenib. The risks of the study are continuously assessed by the MHI's pharmacovigilance department. This risk-benefit will be discussed in periodic safety reports. These reports will include all regulatory aspects and will be submitted to the competent authorities.
ELIGIBILITY CRITERIA	
	Signed informed consent obtained before any study specific procedures
	2. Male or female ≥ 18 years of age
	Histological documentation of adenocarcinoma of the colon or rectum
	Patients with metastatic colorectal cancer
	 Progression during or within 3 months following the last administration of approved standard therapies, which must include a fluoropyrimidine (or raltitrexed), oxaliplatin, irinotecan, anti-VEGF therapy and an anti-EGFR therapy (for RAS wild-type tumors), encorafenib
	6. ECOG performance status ≤1
	7. Life expectancy of at least 3 months
	8. Patients with A/A CCND1 genotype of rs603965 CCND1
	9. Adequate bone marrow, liver and renal function as assessed by the following laboratory requirements conducted within 7 days of starting study treatment:
	➤ Lipase ≤ 1.5 x ULN
	➤ Total bilirubin ≤ 1.5 x ULN
	➤ Alanine aminotransferase (ALT) and aspartate aminotransferase (AST) ≤ 3.0 x ULN (≤ 5 x ULN for patients with liver involvement of their cancer)

- \triangleright Alkaline phosphatase (ALP) ≤ 2.5 x ULN (≤ 5.0 x ULN for patients with liver involvement for their cancer and/or have bone metastases)
- ➤ Platelet count ≥ 100,000/mm3; Hemoglobin (Hb) ≥ 9 g/dL; Absolute neutrophil count (ANC) ≥ 1,500/ mm3. Transfusion to meet the inclusion criterion
- ➤ Serum creatinine ≤ 1.5 x ULN
- 10. International normalized ratio (INR) ≤ 1.5 x ULN and partial thromboplastin time (PTT) or activated partial thromboplastin time (aPTT) ≤ 1.5 x ULN unless receiving treatment with therapeutic anticoagulation. Patients being treated with anticoagulant, e.g., heparin, will be allowed to participate provided no prior evidence of an underlying abnormality in these parameters exists. Close monitoring of at least weekly evaluations will be performed until INR and PTT are stable based on a pre-dose measurement as defined by the local standard of care
- 11. Women of childbearing potential must have a blood or urine pregnancy test performed a maximum of 7 days before start of study treatment, and a negative result must be documented before start of study treatment
- 12. Women of childbearing potential and men must agree to use adequate contraception before entering the study until at least respectively 7 months and 4 months after the last study drug administration of Regorafenib and respectively 6 months and 3 months after the last study drug administration of Irinotecan. The investigator or a designated associate is requested to advise the patient on how to achieve an adequate birth control. Adequate contraception is defined in the study as any medically recommended method (or combination of methods) as per standard of care.

Exclusion criteria

- 1. Patients with A/G or G/G CCND1 genotype of rs603965 CCND1
- 2. Prior treatment with regorafenib or sorafenib
- 3. Prior treatment with TAS 102
- 4. Major surgical procedure, open biopsy, or significant

traumatic injury within 28 days before start of study drug

- Pregnant or breast-feeding subjects. Women of childbearing potential must have a pregnancy test performed a maximum of 7 days before start of treatment, and a negative result must be documented before start of study drug
- 6. Congestive heart failure ≥ New York Heart Association (NYHA) class 2
- 7. Unstable angina (angina symptoms at rest), new-onset angina (begun within the last 3 months)
- 8. Myocardial infarction less than 6 months before start of study drug
- 9. Cardiac arrhythmias requiring anti-arrhythmic therapy (beta blockers or digoxin are permitted)
- Uncontrolled hypertension. (Systolic blood pressure > 140 mmHg or diastolic pressure > 90 mmHg despite optimal medical management)
- 11. Pleural effusion or ascites that causes respiratory compromise (≥ NCI-CTCAE V5.0 Grade 2 dyspnea)
- 12. Ongoing infection > Grade 2 NCI-CTCAE V5.0
- 13. Known history of human immunodeficiency virus (HIV) infection
- 14. Active hepatitis B or C, or chronic hepatitis B or C requiring treatment with antiviral therapy
- 15. Patients with seizure disorder requiring medication
- 16. History of organ allograft
- 17. Patients with evidence or history of any bleeding diathesis, irrespective of severity
- 18. Any hemorrhage or bleeding event ≥ NCI-CTC V5.0 Grade 3 within 4 weeks prior to the start of study medication
- 19. Non-healing wound, ulcer, or bone fracture

- 20. Dehydration NCI-CTCAE V5.0 Grade ≥ 1
- 21. Substance abuse, medical, psychological or social conditions that may interfere with the subject's participation in the study or evaluation of the study results
- 22. Known hypersensitivity to any of the study drugs, study drug classes, or excipients in the formulation
- 23. Any illness or medical conditions that are unstable or could jeopardize the safety of the subject and his/her compliance in the study
- 24. Persistent proteinuria of NCI-CTCAE V5.0 Grade 3 (> 3.5g/24 hours)
- 25. Patients unable to swallow oral medications
- 26. Any malabsorption condition
- 27. Chronic inflammatory bowel disease and / or bowel obstruction
- 28. Unresolved toxicity higher than NCI-CTCAE V.5.0 Grade 1 attributed to any prior therapy/procedure excluding alopecia, hypothyroidism and oxaliplatin induced neurotoxicity ≤ Grade 2
- 29. Concomitant participation or participation within the last 30 days in another clinical trial
- 30. Systemic anticancer therapy during this trial or within 4 weeks before randomization
- 31. Concomitant intake of St. John's wort
- 32. Live attenuated vaccines are prohibited 10 days before the treatment, during the treatment and 6 months after the termination of treatment
- 33. History of gastrointestinal fistula or perforation
- 34. Previous or concurrent cancer that is distinct in primary site or histology from colorectal cancer within 5 years prior to study inclusion, except for curatively treated cervical cancer in situ, non-melanoma skin cancer and superficial

	bladder tumors [Ta (non invasive tumor), Tis (carcinoma in situ) and T1 (lamina propria invasion)].
STUDY PRODUCT OR MEDICAL DEVICE	REGORAFENIB IRINOTECAN
ENROLLMENT PROCEDURE	Pre-treated patients with mCRC and wt or mutated RAS status Randomisation 1 :1 Genotype A/A of cyclin D1 (25% of patients) Arm A: REGIRI (irinotecan + regorafenib) Arm B: Stivarga® (Regorafenib)
TREATMENT OR SURGERY MODALITIES	Experimental arm: REGIRI (arm A) -Irinotecan will be administered every 15 days. -1st cycle: Irinotecan will be administered at the dose of 120 mg/m² on D1 by a IV perfusion over 90 minutes. -2nd cycle: if no diarrheas grade > 1 and any other toxicities grade > 2 then the Irinotecan dose will be at 150 mg/m² and administered on D1 by IV infusion over 90 minutes. -From the third cycle: if no diarrheas grade > 1 and any other toxicity grade > 2 then the Irinotecan dose will be at 180 mg/m² and administered on D1 by IV infusion over 90 minutes. D1=D15 -Regorafenib will be given orally at a dose of 160 mg, once daily during on days 2–8 and 16–22 of each cycle, D1 = D28 → A chemotherapy course = 15 days, 1 cycle = 4 weeks Control arm: STIVARGA® (Regorafenib) (arm B) -Regorafenib will be given orally at a dose of 160 mg once daily over 3 weeks followed by 1 week off, D1=D28. 1 cycle = 4 weeks

ANCILLARY STUDY	Immunohistochemistry: The expression of cyclin D1 protein will be sought by immunohistochemistry on tissue sections obtained from paraffinembedded specimens. We will investigate any association between protein expression and response to treatment. In addition, depending on the progress of knowledge at the time of the study is completed, other biomarkers predictive of response to treatment can be explored by IHC on the same tumor blocks.
STATISTICAL CONSIDERATIONS	To show an increase of median overall survival from 7 to 15 months (30% to 57% rates, respectively), with a HR=0.47 and a power of 80% and alpha=5%, 55 events are required for the 78 patients to be randomized considering 15% additional patients for lost to follow-up. The A/A Cyclin D1 (A/A CCDN1) genotype accounting for 25% of the mCRC patients, a screening of 312 patients will be required before randomization which will be stratified BY RAS status. The inclusion period will last 64 months No interim analysis is planned.
STUDY PERIOD	 First inclusion : september 2019 Inclusion period : 64 months End of the inclusion period: January 2025 Expected end of study: June 2025 Report : December 2025

1. Background and rationale

Until recently, there were no treatment options available for patients with metastatic colorectal cancer who progress after all approved standard therapies, although many patients maintain a good performance status and could be candidates for further therapy.

The NEXIRI combination (sorafenib + irinotecan) showed promising results in heavily pretreated mCRC patients with KRAS mutated tumors (1). A randomized phase II study assessed this combination versus irinotecan or sorafenib as monotherapies, with possible cross-over to the NEXIRI arm at progression for patients treated with either monotherapy. The progression-free survival at two months, the primary objective of the study, was of 59%. The median progression-free survival was of 3.7 months (95% CI: 2.2-4.9) and 3.5 months (95% CI: 2.1-3.7) in the NEXIRI and cross-over arms, and of 1.9 (95% CI: 1.7-2.1) and 2.1 (95% CI: 1.9-2.5) in the irinotecan and sorafenib (monotherapies) groups, respectively. The median overall survival was higher in patients treated with NEXIRI, either from the beginning of the study or at progression (cross-over patients): 7.2 (95% CI: 5.8-9.4) and 7.9 months (95% CI: 7.1-8.7) compared with patients treated only with irinotecan or sorafenib, respectively 3 (95% CI: 2.1-3.8) and 3.3 months (95% CI: 2.5-4.2) (2).

Cyclin D1 (CCND1) is involved in the G1 phase of the cell cycle; the A870G rs603965 polymorphism is specifically associated with response to anti-cancer treatments (3,4). The A/A genotype, which generates a truncated form of CCND1, was favorable to the NEXIRI combination on overall survival, with a median of 19.6 months (95% CI: 4.8-/) versus 6.2 months (95% CI: 4.9-9.4) for the A/G and G/G genotypes; this benefit was not reported in patients treated with sorafenib alone.

This data would have warranted further investigation through a large, randomized phase III trial, however, information was given by Bayer that no clinical development was planned in the indication of mCRC with sorafenib.

Regorafenib is an oral tumor deactivation agent – whose chemical structure is close to that of sorafenib - which potently blocks multiple protein kinases, including kinases involved in tumor angiogenesis, oncogenesis, metastasis and tumor immunity. Unlike sorafenib, regorafenib underwent a clinical development program in GI cancers, showing survival benefits in metastatic colorectal cancer which has progressed after all standard therapies. In the phase III study CORRECT, the addition of regorafenib to best supportive care resulted in significantly longer survival, compared to placebo plus best supportive care, with a p value of 0.005178 from stratified log rank test, a hazard ratio of 0.774 [95% CI 0.636, 0.942]) and a median OS of 6.4 months vs. 5.0 months (5). This study provided evidence for a continuing role of targeted treatment after disease progression, with regorafenib offering a potential new line of therapy in this treatment-refractory population.

Meanwhile, a combination approach was investigated to create potential synergy with the ultimate objective to improve even more survival outcomes in this particular population.

A combination of FOLFOX or FOLFIRI (oxaliplatin 85 mg/m2 or irinotecan 180 mg/m2, D/Lfolinic acid 400 mg/m2, 5-FU bolus 400 mg/m2 followed by 5-FU 2400 mg/m2 for 46 hours) every 2 weeks and regorafenib (160 mg/day administered sequentially to FOLFIRI on days 4-10 and 18-24 of every 4 week cycle, was explored in a phase Ib trial in patients with metastatic colorectal cancer (mCRC) (6). The incidence of drug-related adverse events of any grade was similar (no significant differences) between FOLFOX and FOLFIRI groups indeed Thrombocytopenia (20% vs 20%), Neutropenia was (44% vs 55%), Diarrhea (52% vs 60 %), hand-foot reaction skin reaction (36% vs 35%). The most frequent drug-related adverse events leading to dose modification were neutropenia (n = 12; 27%), mucositis (n = 12) 8; 18%), hand–foot skin reaction (n = 8; 18%), and leukopenia (n = 5; 11%). Regorafenib in combination with mFOLFOX6 or FOLFIRI showed encouraging anti-tumor efficacy with partial response in 7 patients, 4 on regorafenib with mFOLFOX6 and 3 on regorafenib with FOLFIRI. Overall, disease control (i.e., partial response or stable disease) was achieved in 33 patients (87%), 18 on regorafenib with mFOLFOX6 and 15 on regorafenib with FOLFIRI. Even though regorafenib increased the exposure to SN-38 in the FOLFIRI group, it was not associated with reduced tolerability.

These findings were confirmed in a multicenter, randomized, double-blind phase II trial of FOLFIRI plus regorafenib (A) or FOLFIRI + placebo (B) in mCRC, in which the addition of regorafenib on an intermittent schedule (week on, week off) to FOLFIRI as 2nd line therapy, was tolerable, and resulted in a statistically significant prolongation of PFS compared to FOLFIRI alone. Grade \geq 3 adverse events occurring in > 5% of patients (A vs B) included neutropenia (40% vs 30%), diarrhea (14% vs 5%), hypophosphatemia (14% vs 0%), fatigue (11% vs 7%), mucositis (9% vs 10%), hypertension (8% vs 2%), elevated lipase (8% vs 3%) and hand-foot syndrome was grade \geq 5% on arm A vs 2% on B. The addition of regorafenib on an intermittent schedule to FOLFIRI was tolerable, and resulted in a statistically significant prolongation of PFS compared to FOLFIRI alone (7).

Altogether, these results and those of the NEXIRI study justify conducting a phase III randomized trial assessing a regorafenib – irinotecan (REGIRI) combination versus Regorafenib alone in mCRC patients of CCND1 A/A genotype, who have progressed being treated with available therapies.

2. Study objectives and Endpoints

2.1 Objectives

2.1.1 Primary objective

Comparison of overall survival in the Regorafenib and REGIRI combination (Regorafenib + Irinotecan) arms in mCRC patients of Cyclin D1 A/A genotype.

2.1.2 Secondary objective

- Progression-free survival
- Time to deterioration
- Objective response rate
- Disease control
- Toxicity (according to the NCI CTC V5.0)
- Quality of life (EORTC QLQ-C30 appendix 2)

2.2 Endpoints

2.2.1 Primary endpoint

Median Overall survival presented with its confidence interval at 95%, estimated from the randomization date to the date of death, whatever the cause, using the Kaplan-Meier method.

2.2.2 Secondary endpoints

The secondary efficacy endpoints include:

- Progression-free survival (PFS), defined as the time (days) from date of randomization to date of first observed disease progression (investigator's radiological or clinical assessment) or death due to any cause, if death occurs before progression is documented. Patients without tumor progression or death at the time of analysis will be censored at their last date of tumor assessment.
- Time to Deterioration is defined as the time between the date of randomization and the first time the patient has a WHO \geq 2 during treatment.
- Disease control rate (DCR), defined as the rate of patients, whose best response was not progressive disease (i.e., CR, PR or SD), to all randomized patients in the treatment group-Objective response rate (OOR), defined as the rate of patients with CR or PR, to all randomized patients in the treatment group. Patients prematurely discontinuing without an assessment will be considered non-responders for the analysis.

- Safety will be evaluated by clinical and biological means and scored on the NCI-CTCAE version 5.0 scale, performed at each visit (every 2 weeks).
- -Quality of life will be evaluated, based on the EORTC QLQ-C30 questionnaire (appendix 2).

[figure not shown]
3. Experimental plan

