3.1 Study design

[figure not shown]
This is an open, prospective, multicenter, randomized Phase III study.

78 patients will be randomized in several centers.

Experimental arm: REGIRI (arm A)

Control arm: Stivarga® (Regorafenib) (arm B)

First inclusion : september 2019Inclusion period : 64 months

End of the inclusion period: January 2025

Expected end of study: June 2025

Report : December 2025

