5.3 Treatment period

REGIRI or Regorafenib:

After all screening assessments have been completed and the patient's eligibility has been confirmed and documented, the patient will be randomized.

The following assessments should be performed on the first day and day 15 of each cycle (REGIRI) or cycle (Regorafenib) except C1D1 prior to receiving study treatment (+/- 3 days):

- Physical examination with weight, body surface area (if the patient's body weight changes by more than 10 % then BSA will be recalculated for Regorafenib and it will be recalculated for any change of weight for Irinotecan) and vital signs (heart rate, blood pressure)
- ECOG performance status :
- Adverse events documentation (including Start/Stop dates, seriousness, CTC notation and grading, relationship to study drug, outcome and action taken) using CTCAE V5.0
- Concomitant medications (including start/stop dates, dose, indication)
- 12-lead ECG. It will be performed every other cycle (8 weeks if there's no postponed treatment) for both arms
- The following laboratory evaluations are not required at Day 1 of Cycle 1 if these
 were completed within 7 days of starting study drug treatment. Otherwise, these
 laboratory evaluations are required on Day 1 and 15 of each cycle:
 - → CBC with differential should be performed: RBC, hemoglobin, hematocrit, platelet count and WBC. WBC must include differential neutrophil, lymphocyte, monocyte, basophil and eosinophil counts
 - → Coagulation panel: Prothrombin time (PT) or the International Ratio of PT (PT-INR) and Partial Thromboplastin Time (PTT)
 - → Electrolyte panel: sodium, potassium, chloride, calcium
 - → Chemistry panel : albumin, lipase, phosphate, glucose, serum creatinine, clearance calculated according CKD-EPI (appendix 7)
 - → Hepatic panel: Aspartate Amino-Transferase (AST), Alanine Amino-Transferase (ALT), bilirubin (total and direct), GGT, alkaline phosphatase, Lactic Dehydrogenase (LDH)

- → Thyroid function test (TSH, free T3, free T4, on day 1 of each cycle for both arms)
- Tumor markers CEA (Carcino-Embryogenic Antigen), CA 19-9 (carbohydrate Antigen 19-9) every cycle for both treatments
- A β-HCG dosage for women of childbearing potential. Post-menopausal women with no menses for at least 1 year or surgically sterilized women will not be required to undergo a pregnancy test (on day 1 of each cycle for both arms).
- Urine analysis by urinary dipstick. If results of protein ≥ 3+, then quantification

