- Chemistry panel: albumin, lipase, phosphate, glucose, serum creatinine, clearance calculated according CKD-EPI (appendix 7)
- Hepatic panel: Aspartate Amino-Transferase (AST), Alanine Amino-Transferase (ALT), bilirubin (total and direct), GGT, alkaline phosphatase, Lactic Dehydrogenase (LDH)
- Urine analysis by urinary dipstick. If results of protein ≥ 3+, then quantification of proteinuria on a 24-hour urine collection must be done.
- Drug accountability (pharmacy)
 Verify patient's diary. It will allow to patient to write down his oral intakes and blood pressure values

The following assessments should be performed on day 15 of cycle 1 and 2:

Stivarga® (Regorafenib - arm B):

• these laboratory evaluations are required: Aspartate Amino-Transferase (AST), Alanine Amino-Transferase (ALT), bilirubin (total and direct)

The following assessments should be performed on day 22 of cycle 1 and 2:

REGIRI (arm A):

- Phone call by a treatment nurse for knowing if there are any adverse events and blood pressure value (current state of the art)
- These laboratory evaluations are required: Aspartate Amino-Transferase (AST),
 Alanine Amino-Transferase (ALT), bilirubin (total and direct)

The following assessments should be performed at each evaluation i.e (every 8 weeks):

REGIRI or Regorafenib:

 Tumor markers CEA (Carcino-Embryogenic Antigen), CA 19.9 (Carbohydrate Antigen 19-9)

 Radiological tumor assessment using the RECIST criteria, version 1.1 (see Appendix 5) must be performed. (CT scan of the abdomen, pelvis and chest or hepatic MRI and CT scan of the pelvis and chest without injection)

A PET scan is not acceptable for radiological evaluation. Throughout the study, the identical lesions to those identified and measured at baseline must be evaluated using the same technique, and preferably by the same radiologist. Copies of all CT scans performed for tumor assessment in non-progressive enrolled patients will be stored on CDs at the site

 EORTC QLQ-C30 (appendix 2) questionnaires will be completed by the patient at each evaluation i.e 8 weeks

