5.4 End of treatment Visit

When a patient is taken off treatment, the following assessments should be performed within 14 days after study treatment has stopped provided the last clinical and laboratory

evaluations > 7 days.

- Physical examination with weight, BSA and vital signs (heart rate, blood pressure)
- ECOG performance status
- Adverse events documentation (including Start/Stop dates, seriousness, CTC notation and grading, relationship to study drug, outcome and action taken) using CTCAE V5.0
- Concomitant medications
- 12 lead ECG

- A CBC with differential should be performed: RBC, hemoglobin, hematocrit, platelet count and WBC. WBC must include differential neutrophil, lymphocyte, monocyte, basophil and eosinophil counts
- Coagulation panel: Prothrombin time (PT) or the International Ratio of PT (PT-INR) and Partial Thromboplastin Time (PTT)
- Electrolyte panel: sodium, potassium, chloride and calcium
- Chemistry panel: albumin, lipase, phosphate, glucose, serum, creatinine, clearance calculated according CKD-EPI (appendix 7)
- Liver function test panel: Aspartate Amino-Transferase (AST), Alanine Amino-Transferase (ALT), bilirubin (total and direct), GGT, alkaline phosphatase, Lactic Dehydrogenase (LDH)
- Thyroid function test: TSH, free T3, and free T4
- Tumor markers: CEA (Carcino-Embryogenic Antigen), CA 19.9 (Carbohydrate Antigen 19-9)
- Urine analysis by urinary dipstick. If results of protein ≥ 3, then quantification
 of proteinuria on a 24-hour urine collection must be done
- A radiological tumor assessment using the RECIST criteria, version 1.1 (see Appendix 5) must be performed if the last radiological assessment > 1 months. (CT scan of the abdomen, pelvis and chest or hepatic MRI and CT scan of the pelvis and chest without injection)
- Drug accountability (pharmacy)

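### PFS counts an open-label investigator's undefined clinical progression as an event, and no planned analysis would show whether a PFS difference depends on such calls

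*Combined protocol and SAP*

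**What the plan says.** The synopsis and Section 2.2.2 count as a PFS event the "date of first observed disease progression (investigator's radiological or clinical assessment) or death due to any cause". On censoring, Section 2.2.2 adds: "Patients without tumor progression or death at the time of analysis will be censored at their last date of tumor assessment". Section 3.1 states: "This is an open, prospective, multicenter, randomized Phase III study".

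The only tumour assessment described is the "Radiological tumor assessment using the RECIST criteria, version 1.1", which Section 5.3 places in both arms under "The following assessments should be performed at each evaluation i.e (every 8 weeks". A further scan at end of treatment "must be performed if the last radiological assessment > 1 months"; Section 5.5 requires it at the 30-day visit if it was not done then. After that visit only vital status and anti-cancer drugs are followed.

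The documents disagree on clinic visits:

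- The Section 5.1 table appears to mark physical examination and ECOG on D1 and D15 for REGIRI but on D1 only for regorafenib.
- The cycle 1-2 lists in Section 5.3 point the same way. On D15, REGIRI has an examination and ECOG, and regorafenib has AST, ALT and bilirubin only.
- The opening list of Section 5.3 reads: "The following assessments should be performed on the first day and day 15 of each cycle (REGIRI) or cycle (Regorafenib". This can be taken as D1 and D15 in both arms.
- The safety item in Section 2.2.2 speaks of two-weekly visits without naming an arm.

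Section 9.3 compares PFS by a log-rank test stratified by RAS, with a hazard ratio. The sensitivity analyses in Sections 9.2 and 9.3 that name an endpoint concern OS. The quality-of-life text mentions others without saying what they are. None is named for PFS.

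**The concern.** Imaging on a common 8-week grid treats the two arms alike. A clinical call need not. It is made by someone who knows the treatment, against no stated criterion, and the text does not limit when it may be made, so it can date an event between scans. If investigators are readier to call progression in one arm, or simply see one arm more often, the PFS curves can separate when the tumours behave identically.

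PFS is the first secondary efficacy endpoint listed and is formally tested. As planned, the report would contain one PFS hazard ratio and nothing to tell a reader whether it rests on scans or on unblinded clinical judgement.

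**Working it through.** The plan gives no expected PFS, PFS effect or PFS power, so there is no figure of its own to reproduce. The check asks what happens to PFS when true progression is identical in both arms.

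**Inputs from the documents**

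- Scans every 8 weeks in both arms (5.3).
- 39 patients per arm (9.1: 68 × 1.15 = 78.2, taken as 78 = 2 × 39).
- Visits between scans every 2 weeks on REGIRI and every 4 weeks on regorafenib under the Section 5.1 reading, or the same in both arms under the other reading.
- Median time to progression of 2.0 or 3.5 months (8.7 or 15.2 weeks), close to the earlier medians in Section 1: 1.9-2.1 months on monotherapy and 3.5-3.7 on sorafenib-irinotecan.

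**Assumed, not in the documents:** exponential progression times, no censoring, no separate deaths, and all calling rates.

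**Model 1: a fixed share of progressions is open to a clinical call.** True progression time T has rate ln 2 / median. The scan dates the event at 8 × ceil(T/8) weeks. With probability q it is dated instead at the next visit, v × ceil(T/v), with v = 2 or 4 weeks. Large-sample Cox HR, REGIRI to regorafenib, Breslow ties:

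| Scenario | Median 2.0 mo | Median 3.5 mo |
|---|---|---|
| Imaging only, both arms | 1.00 | 1.00 |
| Calls in control only, v = 4, q = 20% | 0.95 | 0.97 |
| Calls in control only, v = 4, q = 40% | 0.90 | 0.94 |
| Calls in both arms, v = 2 vs 4, q = 20% | 1.02 | 1.01 |
| Calls in both arms, v = 2 vs 4, q = 40% | 1.04 | 1.03 |

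Efron ties bring every value slightly nearer 1 (control-only calls: 0.93-0.98).

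**Model 2: a calling probability p at each between-scan visit after true progression.** 4,000 trials of 39 per arm, unstratified two-sided 5% log-rank test:

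| Scenario | HR, 2.0 / 3.5 mo | Rejection, 2.0 / 3.5 mo |
|---|---|---|
| Imaging only | 1.00 / 1.00 | 4.8% / 5.2% |
| Same 4-weekly visits, p = 0.5 in both arms | 1.00 / 1.00 | 5.5% / 6.3% |
| Visits 2- vs 4-weekly, p = 0.5 in both arms | 1.13 / 1.07 | 9.0% / 6.7% |
| Same 2-weekly visits, p = 0.1 REGIRI, 0.5 control | 0.83 / 0.90 | 16.4% / 8.2% |
| Control only, 4-weekly, p = 0.5 | 0.88 / 0.92 | 11.2% / 6.7% |

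Model 2 moves further because it lets more progressions be called. At p = 0.5, three between-scan visits catch up to 1 − 0.5³ = 87.5% of the earliest progressors in a scan interval and one visit catches 50%, against a cap of 20-40% in Model 1. Adding control-arm calls before true progression, at 5-10% per visit, takes the last row to HR 0.81-0.71.

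**Reading the results.** Imaging-only events keep the HR at 1. So do equal visits with equal calling. More frequent visits on REGIRI push the HR above 1; readier calling in control pushes it below 1. The censoring rule was not simulated separately.

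**The case against.** **Size.** The departures are driven by assumptions. An HR of 0.90-0.97 needs clinical calls in control patients and none on REGIRI. With 39 per arm and an event in every patient, the standard error of the log HR is √(4/78) = 0.23, so the 95% interval spans a factor of exp(1.96 × 0.226) = 1.56 each way. This stands: the bias may be small beside the noise, and its existence is not shown.

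**Existing safeguards.** The scan rules in Sections 5.4 and 5.5 should put an image close to most clinical calls that stop treatment. Appendix 5 is not in the text, and Section 9.3 says a SAP is still to be written, so a criterion or a PFS sensitivity analysis may yet appear. This also stands in part, but nothing in the text makes those scans decide or date the event.

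Some stronger readings are tempting but not supported:

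- **Events can fall at any visit while censoring is tied to scans only, so a patient leaving at week 6 is censored at baseline.** Section 2.2.2 says tumour assessment without specifying imaging; scan-only censoring is an inference from the only assessment described. The week-6 case also needs a patient who is lost or withdraws without the required scan, because Section 8.1 keeps patients who stop treatment in the trial.
- **Scans behind progression calls cannot be checked.** Section 5.3 says: "Copies of all CT scans performed for tumor assessment in non-progressive enrolled patients will be stored on CDs at the site". That sentence does not require copies for progressors, but it does not show that their scans are unavailable. Sections 11.2 to 12.1 provide access to patient files and source documents, and archiving.
- **Medians would shift by about a month.** At a 2.0-month median, 1 − 2^(−8/8.7) = 47% have progressed by the week-8 scan. Adding 20-40% of those progressing in weeks 8-12 gives only 50-53% by week 12. A median that jumps from week 16 to week 12 on that change reflects the scan grid, not the size of the bias.
- **Imaging-only PFS should become the main definition.** Patients who deteriorate clinically without RECIST confirmation would then count only at death or be informatively censored. With earlier monotherapy medians near 2 months and an 8-week scan interval, that loss is plausible.

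**Conclusion.** The concern holds in a limited form. An undefined clinical call by an unblinded investigator is a full PFS event, clinical contact may differ by arm, and no named analysis would expose unequal calling. PFS could then differ with identical tumour growth. The direction is not fixed: readier calling in control favours REGIRI, and closer contact on REGIRI works against it.

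The size cannot be fixed from the documents. Illustrative HRs are about 0.90-0.97 for control-only calls on a 20-40% share and 1.01-1.04 for visit frequency alone. Stronger assumed rates give about 0.83 to 1.13, or lower if calls precede true progression. The visit-frequency component rests on the Section 5.1 reading of the schedule and disappears if visits are the same in both arms.

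OS, the primary endpoint, is unaffected. The point concerns how far a PFS result could be trusted; it is not evidence that the result will be biased.

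**What to change.** 1. In Section 9.3, keep the current PFS definition and prespecify a second PFS analysis. Its event is RECIST 1.1 progression on imaging, including the end-of-treatment or 30-day scan, or death. Censor at the last radiological assessment, or at randomisation if there is none after baseline.
2. Report by arm the number of clinical-only progressions, meaning those declared by the investigator with no RECIST progression on any scan up to and including the end-of-treatment or 30-day scan.
3. State that the PFS conclusion depends on whether the two analyses agree.
4. Reconcile the visit schedules in Sections 5.1 and 5.3, so that the intended clinical contact in each arm is clear.

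The cost is protocol or SAP wording and one extra analysis on scans already required. The added analysis may censor informatively those clinical progressors whom imaging does not confirm, which is why it accompanies the current definition and does not replace it. With the SAP still to be written before database lock, it can be prespecified there.
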